LONG TERM DATA COLLECTION FOR THE EVALUATION OF INCIDENCE AND BREAST CANCER SPECIFIC MORTALITY VIA INTERROGATION OF DATA COUNTRY-SPECIFIC HEALTH INSURANCE AND SCREENING STRUCTURES DATA BASES (NOT INTERVENTIONAL, NOT PART OF THE STUDY FOLLOW-UP): UP TO 15-YEARS FROM STUDY ENTRY

DURATION UNTIL PRIMARY ENDPOINT EVALUATION (INCLUSION + FOLLOW-UP) : 6.5 YEARS

H) STUDY SCHEME/OUTLINE

I) SCHEDULE OF ACTIVITIES (SOA)

VISITS	Who will record the data into the web-platform	Baseline	Risk-based screening arm	Follow-up			
				NA	NA	NA	NA
Visits n°		Visit (V0)	V1	M12 V0 + 12 +/- 6 months	M24 V0 + 24 +/- 6 months	M36 V0 + 36 +/- 6 months	M48 V0 + 48 +/- 6 months
Visit / Follow up timepoints Dates		D0	V0 + 8-12 weeks				
Type of visit		physical	physical or telephone call	On-line	On-line	On-line	On-line
Inclusion/non-inclusion criteria	investigator	X					
Signed informed consent form	Investigator/Woman	X					
Baseline mammogram (if applicable)		X*					
Minimal medical data	investigator	X					
Randomization	investigator	X					
Medical history	investigator/Woman	X					
Result of risk score (only for risk-based screening)	investigator		X				
Study visit	NA	X [#]	X [§]				
Study mammogram	NA	(X) [£]	(X) [£]	(X) [£]	(X) [£]	(X) [£]	(X) [£]
BIOLOGICAL TEST (only for women who will be randomized in the risk-based screening arm)							
Saliva test		X					
QUESTIONNAIRES							
1. STAI short form (state anxiety)	Woman	X	X	X			X
2. Comprehension questionnaire	Woman	X	X				X
3. Information seeking-behavior questionnaire	Woman		X				X
4. Quality of life (EQ-5D)	Woman	X					X
5. Satisfaction	Woman			X			X
6. Socio-demographic and economic status questionnaire	Woman	X					X
FOLLOW-UP DATA							
Mammogram yes/no + results	Woman/ OBSS or national security social			X	X	X	X
Breast US (or ABUS) yes/no + results	Woman/ OBSS or national security social			X	X	X	X
Breast MRI yes/no + results	Woman/ OBSS or national security social			X	X	X	X
Breast biopsy or surgery + result and date	Woman/ OBSS or national security social			X	X	X	X
Breast cancer yes/no + date	Woman/ OBSS or national security social			X	X	X	X
Other major medical problem yes/no + date	Woman/ OBSS or national security social			X	X	X	X

* Reference mammograms up to 2 year prior to inclusion are accepted

For woman who will have the standard of care screening program

§ For woman who will have the risk-based screening program

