There will be no study entry mammograms. Upon enrolling in the trial and receiving a screening recommendation, each woman's next future mammogram will be scheduled. This will be dated from the date of her most recent mammogram in the two years prior to enrollment into the trial. For example, a woman who had a mammogram 3 months prior to study entry and received an annual screening recommendation would be invited to screen again 9 months after enrollment into the study. A woman who had a mammogram the year prior to study entry who receives a bi-annual screening recommendation would be invited to screen again one year after enrollment into the study.

Women who have not received a mammogram in the two years prior to enrollment may receive a mammogram at study entry if this is standard in their allocated arm and risk level (for risk-based arm).

For women assigned to the risk based screening arm who are less than 50 years of age and had no prior mammogram, the risk score will be evaluated based on the BIRADS density of D (Extremely Dense). If this assumption elevates her risk and results in a more intensive screening recommendation as compared with assuming the lowest BIRADS density, she will receive a study entry mammogram to accurately assess her risk and provide an appropriate screening recommendation. Otherwise, women who receive a screening recommendation of "No repeat screening until age 50", will not receive a study entry mammogram and will not be scheduled to receive a study mammogram until their exit mammogram unless their screening recommendation changes during the course of the study.

End of study mammogram

A study exit mammogram will be planned ONLY for the following women:

- Women in the risk-based screening arm who have been categorized as low risk (no planned mammogram during the course of the study);
- Women in the standard screening arm who had no screening mammogram during the 4-year study period given their age.

All these women will have a mandatory end-of-study mammogram at 4 years

For all the other women, the last mammography scheduled during the 4-year follow-up will be considered as the end-of-study mammography.

Organization within specific regions in the participating countries

This trial uses the existing national/regional screening structures for potential participants' information, accrual, data retrieval and follow-up. This is crucial for organizational reasons, in order not to disrupt existing pathways;

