1.2 Benefit-risk assessment

As demonstrated above, risk-based breast cancer screening is highly promising, given its potential ability to allow more screening efficacy in those who derive any benefit of such screening because of a higher breast cancer risk, together with decreasing harm in women who might not derive benefit from mammogram given their low personal breast cancer risk.

However, risk zero does not exist, and it is important to verify that a positive benefit-harm ratio is maintained for all participants throughout the trial.

The individual potential benefits and harms will be carefully explained to participants throughout the trial. They are explained in the informed consent, to allow women to make their own decision regarding not only participation to MyPeBS trial, but somehow also to screening in general.

Risk reduction measures will be maintained throughout the trial:

Trial-level risk reducing measures will always be applied to maximise the benefit-harm ratio for all (yearly reassessment of risk, reminders, 4-year mammogram for all, careful surveillance of the trial by the Ethics and Data Monitoring Committee, ...). Breast cancer awareness will be repeatedly stimulated for all participants throughout the trial. This is will even more pronounced for women in the low-risk group of the risk-based arm, who will have their next mammogram after 4 years.

1.2.1 *Effects and risks of mammography screening in the standard arm*

The benefits and harms/risks from standard mammographic screening have been extensively described in 1.1.2. We summarize them below:

- Mammographic screening has been associated with an average 20% reduction in breast cancer-specific mortality in average risk-women: The available evidence is derived from 11 randomized trials and their meta-analysis with 13 years of follow-up: The benefit is demonstrated for women over 50, while 2 studies demonstrated benefit for women aged 40-49, and others were negative, leading to divergent interpretation and recommendations throughout countries. Of note, the relative reduction in breast cancer specific mortality appears higher for women actually attending screening. Trials indicated no statistically significant reductions in all-cause mortality with screening. Risk for higher-stage breast cancer was reduced for age 50 years and older (RR 0.62 [95% CI, 0.46 to 0.83]; 3 trials), but not for age 39 to 49 years old (RR 0.98 [95% CI, 0.74 to 1.37]; 4 trials).

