1.2.3 Potential risks from the participation in the risk-based arm

Small increase in stage 2 or higher breast cancers in women identified at low-risk

Such women are at low but not null breast cancer risk. 87 breast cancers are expected in women for whom only 4-yearly mammogram will be planned (low-risk), but for 41 of these women, the standard is an absence of mammogram since they are aged 50 or less. Only 46 cancers are expected in low risk women for whom the current standard would be to do bi-yearly mammogram, and who will get 4-yearly mammogram instead (light orange in the table above). According to the most pessimistic estimation an excess of 5 stage 2 or higher breast cancers may therefore be observed in these low-risk women.

This potential increase must be prevented by specific dedicated measures including information of participants in this group, repeated and careful breast awareness and annual reassessment of risk.

Increase in false positive recalls and overdiagnosis in high-risk women and in women less than 50 undergoing end of study mammogram

Overall, we should observe an increase in false positive recalls among these patients. The rate of such events is hardly evaluable, since such recalls are proportionally less frequent in women undergoing yearly mammograms than those getting bi-annual screening. It could be around 500 additional false positive findings. As well, there should be an increase in potentially overdiagnosed breast cancers, although such events appear rarer among high-risk individuals.

Increase in anxiety from risk identification and from additional screening images in the high risk women

It might happen, but is not certain, that the identification of a high-risk situation can cause anxiety or distress. From previous studies, it seems this anxiety is transient and low. This will be carefully scrutinized throughout the study with interim analyses of psychological safety.

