The individual breast cancer risk will be estimated using the modified Mammorisk™ (by inclusion of SNPs) or, if more than one first degree family history of breast/ovarian cancer, using the modified Tyrer Cuzick™ score, both including polymorphism risk score.

Breast cancer risk levels will to be classified into 4 meaningful categories, which have been defined by the clinical trial steering committee, according to available guidelines and published literature (see 1.1.9).

Statlife is in charge of the centralized and automated software dedicated to risk evaluation. Their module will automatically extract all necessary variables from the central database and incorporate the polygenic score once available, as well as mammographic density.

Statlife will transfer the final risk score of each participant upon availability, to the investigator, who will be in charge of transmitting the result to the participant. The bases of risk calculation will be available on the result

sheet for each participant. The result of the polygenic risk score will also be available and transmitted. Results will be transparently transmitted to allow for awareness and empowerment of participants.

The risk categories estimated using the risk models or identified in other situations, are listed in the Table below.

What if some data is missing?

- If genotyping is not available (failure of technique, participant's refusal), the personal risk will be estimated by the risk score alone (clinical variables + mammographic density)
- If mammographic density is not available:
 - If the participant is 50 years old or more, a baseline mammogram will be mandatory, that will allow density evaluation
 - If the participant is 40-49 years old, the maximum density-linked risk will be applied (BI-RADS class D)
 - If one or two clinical data are not available: risk should be estimated without this information

Risk recalculations

Of note, risk recalculation may occur during the 4-years follow-up of each patient and will be conducted the same way. This may occur if:

- Participant/investigator declares a significant event that may change the participant's risk level (breast biopsy with benign diagnosis, diagnosis of atypical lesion, identification of the participant as a carrier of a germline mutation of a high penetrance gene)

- Identification of a new, major risk polymorphism that would be incorporated in the polygenic risk score

Risk level	Low risk	Average risk	High risk	Very high risk

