5.2.5 Breast Cancer Screening in the risk-based arm

In the risk-based arm, women are screened in a risk-based fashion:

Screening recommendations in each risk category are as described in the Table below.

- Women identified at low risk will not have any mammogram until an end of study mammogram at 4 years.
- Women at average risk will have a mammogram every 2 years
- Women at high risk will have a yearly mammogram
- Women at very high risk will have a yearly mammogram + yearly MRI until age 60. Both shall be performed at the same time period, MRI being performed before mammogram.
- Breast US is proposed in women with dense breasts, according to national guidelines

2D digital mammogram may be replaced by tomosynthesis according to the country's, regions' and centers' policy.

Definition of risk thresholds and breast cancer screening scheme in the **risk-based** arm are summarized below:

Risk-based arm				
Risk level	Low risk	Average risk	High risk	Very high risk
Numerical definition (invasive breast cancer risk at 5 years)	< 1%	1-1.66%	$\geq 1.67\%$ and < 6%	$\geq 6\%$ at 5 years
Mammogram*	1 at end of study	Every 2 years	Yearly	Yearly
Additional	Yearly breast cancer awareness reminder	High density: US or ABUS every 2 years	High density: US or ABUS every year	Annual MRI until age 60

* Or Tomosynthesis + synthetic 2D if applicable in the country/center

The participants' screening schedules will be organized according to the date of their last previous

mammogram, as described in the Table below:

		Planned initial Mammogram/ DBT schedule		
		Every 2 years	Yearly	Yearly
Schedule of first screening mammo/DBT according to previous mammogram	No previous mammogram	immediately	immediately	immediately
	Previous mammogram < 1 year	2 years from previous one	1 year from previous one	1 year from previous one
	Previous mammogram between 1 and 2 years	2 years from previous one	immediately	immediately
	Previous mammogram > 2 years	immediately	immediately	immediately

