12.3 Security of participants

Participants classified into the “low risk” category (and above the onset age for standard breast screening in their country) will have less frequent breast imaging comparatively to standard practices; for these participants, the detection of potential cancer could be delayed of a maximum of 2 years as compared to the standard screening frequency (also see section 1.2.3. of the protocol).

Therefore, specific risk reduction measures will be put in place in this subgroup of patients:

- Breast cancer awareness remains a major cornerstone of the reduction of the risk of advanced breast cancer: women must be advised of both symptoms leading to see a doctor and eventually to have a diagnostic mammogram and health behaviors leading to reduced risks of breast cancer (see below)
- Participants with a low risk estimation will be specifically sensitized by investigators to the fact that low risk is not an absence of risk. They will be yearly reminded of this point.
- All participants will be taught which breast symptoms must lead to see a doctor.
- All participants will be yearly reminded that mammograms can miss some cancers and that, therefore, seeing a doctor in case of a symptom remains crucial.
- Breast self-palpation will be taught to women who ask for it only

All cancers detected in this risk-based group will be reviewed at EDMC meeting (Ethics and Data Monitoring Committee, which shall meet at least once a year during the whole study duration and shall review the events of special interest collected throughout the study) with the objective of continuously evaluating whether this subgroup of participants is not too much disadvantaged by their participating to the study.

12.4 Annual safety report.

Events of special interest will be discussed during the EDMC, the minutes of this meeting will specify the number and frequency of breast cancers occurred in the overall included population and in the considered “low risk” subgroup as well as the stage of the cancer and evaluate if these participants are disadvantaged or not.

The annual safety report will include all available safety information and minutes of EDMC. This report will be sent to the competent authority and to the Ethics Committee of each country, according to local regulations.

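### The 2-year maximum detection delay stated for low-risk women is exceeded under the protocol's own scheduling rules, and its worst-case excess of 5 advanced cancers is not a worst case

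*Protocol*

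**What the plan says.** Section 12.3 covers women classed as low risk who are above the onset age for standard screening. It states that for them "the detection of potential cancer could be delayed of a maximum of 2 years as compared to the standard screening frequency", and it refers to section 1.2.3.

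The schedules behind that sentence are set elsewhere:

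- **Low-risk women, section 5.2.5:** "Women identified at low risk will not have any mammogram until an end of study mammogram at 4 years".
- **Other schedules, section 1.1.14:** there is no study entry mammogram as such. Of the next mammogram it says "This will be dated from the date of her most recent mammogram in the two years prior to enrollment into the trial". Its example is a woman on a two-yearly recommendation whose last mammogram was a year before entry; she "would be invited to screen again one year after enrollment into the study".
- **Age of the last mammogram, synopsis (schedule of activities):** "Reference mammograms up to 2 year prior to inclusion are accepted".
- **Baseline mammogram in the risk-based arm, section 5.2.3, where density is unavailable:** "If the participant is 50 years old or more, a baseline mammogram will be mandatory, that will allow density evaluation".
- **Standard intervals, section 5.1:** two-yearly at 50-70 in France, Belgium, Italy and Israel; three-yearly at 50-70 in the UK; yearly at 45-49 in some Italian regions.

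On the number of cancers, section 1.2.3 expects 46 in low-risk women who would otherwise be screened every two years. It concludes: "According to the most pessimistic estimation an excess of 5 stage 2 or higher breast cancers may therefore be observed". It gives neither a stage share nor a relative risk for that step. Section 1.2.2.1, on the benefit side, expects 50 stage 2+ cancers avoided among 329 cancers in women who are screened more. Section 1.2.1 reports: "Risk for higher-stage breast cancer was reduced for age 50 years and older (RR 0.62 [95% CI, 0.46 to 0.83]; 3 trials".

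**The concern.** Two years is what remains when a two-yearly interval is subtracted from a four-yearly one. It is the longest calendar delay only if the standard clock starts at entry. Under section 1.1.14 it starts at the last mammogram, so many women in the standard arm are due well before year 2, while a low-risk woman waits until year 4 whenever she was last screened.

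The excess of 5 raises a related question. It is presented as a worst case, yet it implies a weaker effect of screening intensity than the one the protocol uses to project benefit.

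Both statements concern the only participants whose screening is reduced, and both err in the favourable direction. Section 12.3 is the safety text for this group, so a stated maximum there should not be exceeded by the protocol's own worked example.

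**Working it through.** **1. Delay**

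Let I be the standard interval in months (section 5.1) and m the months from last mammogram to entry, with m from 0 to 24 (synopsis, section 1.1.14). Assume density is available, so that no baseline mammogram is required (section 5.2.3).

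- First standard screen falls at month I − m, or at entry if that is already past.
- First low-risk screen falls at month 48 (section 5.2.5).
- Delay = 48 − (I − m).

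The plan's figure first: I = 24 and m = 0 give 48 − 24 = 24 months, the stated 2 years.

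| Standard schedule | Formula | m = 0 | m = 12 | m = 24 | Range |
|---|---|---|---|---|---|
| Two-yearly (I = 24) | 24 + m | 24 | 36 | 48 | 24 to 48 |
| UK three-yearly (I = 36) | 12 + m | 12 | 24 | 36 | 12 to 36 |
| Yearly, some Italian regions, 45-49 (I = 12) | 36 + m, capped at 48 | 36 | 48 | 48 | 36 to 48 |

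The example in section 1.1.14 is the two-yearly row at m = 12: 36 months. A pure comparison of frequencies does not rescue the maximum either, since four-yearly against yearly is 3 years at m = 0.

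Where a baseline mammogram is taken, the low-risk woman is screened at about month 0 and again at month 48. Against a two-yearly standard the later maximum is then about 24 months, as stated.

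**2. The base of 46 cancers**

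Expected cancers = women × share at that risk level × 5-year risk × 4/5 (tables in sections 1.1.15 and 1.2.2.1).

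- Low risk, 50-59: 19,125 × 0.28 × 0.008 × 0.8 = 34.3.
- Low risk, 60+: 12,750 × 0.15 × 0.008 × 0.8 = 12.2.
- The table's rounded entries give 34 + 12 = 46. The benefit-side base also reproduces: 30 + 29 + 141 + 129 = 329.

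**3. The excess of 5**

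- As stated: 5/46 = 10.9% of the cancers.
- At the protocol's own benefit rate: 50/329 = 15.2%, and 46 × 50/329 = 7.0.
- From a stage share and relative risk: section 1.1.2 puts about one fourth of cancers in regularly screened women at stage 2 or more, so 46 × 0.25 = 11.5. Excess = 11.5/RR − 11.5.
  - RR 0.62: 7.05.
  - RR 0.46: 13.5.
  - RR 0.83: 2.4.
- To obtain 5 by this route: RR = 11.5/16.5 = 0.70, a milder effect than the reported point estimate.

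**The case against.** The strongest defence is that section 12.3 compares with the standard screening frequency and refers to section 1.2.3, which contrasts two-yearly with four-yearly mammography. As interval arithmetic, 2 years is right, and the schedules themselves are openly stated. This explains where the figure came from. It does not support calling it a maximum, because the protocol's own example gives 3 years.

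A reader might infer that low-risk women in general face a 4-year delay. The documents do not support that. Forty-eight months needs a mammogram about 24 months old under a two-yearly standard, or at least 12 months old under a yearly one. It also needs a cancer visible at the first standard screen that stays without symptoms until year 4. For UK women screened within 12 months of entry, 2 years does hold as a cap. Nor should 6 months be added for the month-48 window: the schedule of activities gives the same tolerance to the earlier time points, so the standard screen can move as well.

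A reader might also take the excess to be shown too low, perhaps reaching 21. That value comes from a 38.5% stage share (42,500 × 4 × 0.0012 = 204, over 530 cancers) with RR 0.46: 46 × 0.385 = 17.7, and 17.7/0.46 − 17.7 = 20.8. It does not stand as the protocol's own worst case. The underlying rate includes women under 50 and cancers in unscreened women (section 8.1), so dividing by RR partly counts non-screening twice. The RR contrasts screening with no screening, whereas these women still have a four-yearly mammogram. In a cohort cited in section 1.1.8, low-risk women had 18% of all cancers but 15% of stage 2+ cancers. Scaling one fourth by 15/18 gives 46 × 0.25 × 15/18 = 9.6 and, at RR 0.62, an excess of 5.9. Five is therefore within reach as a central value.

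Finally, one might infer that acceptance of de-escalation, or the monitoring committee's judgement, rests on these two figures. The protocol does not say so. Its rationale is in sections 1.1.9, 1.1.10 and 1.1.14, and under sections 12.3 and 12.4 the committee reviews the cancers actually observed, with number, frequency and stage.

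**Conclusion.** The stated maximum is wrong as a general statement. Under the protocol's rules, and without a baseline mammogram, the longest delay is 48 months against a two-yearly standard, 36 months in the UK and 48 months where Italian regions screen yearly at 45-49. These are upper limits, not typical delays; the protocol does not give the distribution of time since last mammogram, so no average is offered.

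The excess of 5 is unsupported rather than shown to be false. It lies below the 7.0 implied by the benefit-side rate and well inside the range of about 2 to 13.5 from one fourth stage 2+ and the reported confidence interval. The 7.0 assumes that reducing screening costs advanced cancers at the rate at which increasing it saves them; the range applies an RR against no screening. Either way, 5 cannot be called the most pessimistic estimate.

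No endpoint, sample size, analysis or monitoring rule depends on either figure. The point still needs correcting, because it concerns the safety statement for the group whose screening is reduced.

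**What to change.** - **Section 12.3:** reconcile it with the schedule of activities and sections 1.1.14, 5.1, 5.2.3 and 5.2.5. If those schedules stand as written, replace the single 2-year maximum with the one implied for each standard schedule, stating the dependence on time since last mammogram and on whether a baseline mammogram is taken.
- **Section 1.2.3:** either drop the claim that 5 is the most pessimistic estimate, or re-derive the excess as a range with its stage share and effect size shown, on assumptions consistent with section 1.2.2.1.
- **Downstream:** use the corrected figures in reports to the Ethics and Data Monitoring Committee, and in participant information wherever it repeats them (that text was not available here).

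The cost is a text amendment and, if needed, an update of participant information. The stated risk becomes less favourable. No change to any screening schedule is proposed, and which passage should prevail is for the sponsor to settle.

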Participating women will receive standardized self-awareness recommendations, although they will remain free to comply with them. They will be informed on potential risk-reducing strategies associated with their individual breast cancer risk level and individual risk factors. Upon risk calculation, they will receive a printed + online document summarizing all their personal information, risk category assignment, proposed screening strategy, but also suggested personalized risk-reduction measures (such as avoidance of certain endocrine therapies, dietary and exercise recommendations, etc). These measures have been predefined by the trial steering committee.

Participants will be able to retrieve all their personal information from their personal account on the study's web-platform. They also will be able to consult more general information on the project's website.

Table 2: **BREAST CANCER SCREENING SCHEME IN THE STANDARD ARM**

Standard arm (either no mammogram or mammogram(s)/1-2-3 years according to age and country – will be defined individually at study entry in the trial)				
Population	40-49 (France, Belgium, UK and Israel) 40-44 (All women of Italy) 45-49 (for some women depending the region of Italy)	50-70 (UK)	50-70 (France, Belgium, Italy and Israel)	45-49 (Some regions of Italy)
Planned images	No mammogram	Mammogram* every 3 years	Mammogram* every 2 years	Mammogram* every year

* Or Tomosynthesis + synthetic 2D if applicable in the country/center

Table 3: DEFINITION OF RISK THRESHOLDS IN MYPeBS AND **BREAST CANCER SCREENING SCHEME IN THE RISK-BASED ARM**

Risk-based arm				
Risk level	Low risk	Average risk	High risk	Very high risk
Numerical definition (invasive breast cancer risk at 5 years)	<1%	1-1.66%	$\geq 1.67\%$ and <6%	$\geq 6\%$ at 5 years
Mammogram*	1 at end of study	Every 2 years	Yearly	Yearly
Additional	Yearly breast cancer awareness reminder	High density: US or ABUS every 2 years	High density: US or ABUS every year	Annual MRI until age 60

* Or Tomosynthesis + synthetic 2D if applicable in the country/center

F) SAMPLES COLLECTED

SAMPLE TYPES: SALIVA SAMPLES

SAMPLE QUANTITIES: one sample of saliva at baseline for all women randomized into the risk-based screening arm

G) STUDY DURATION

[figure not shown]
INCLUSION PERIOD: 2.5 YEARS

STUDY FOLLOW-UP DURATION (FOR EACH WOMAN IN BOTH GROUPS): 4 YEARS

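### The 2-year maximum detection delay that protocol section 12.3 gives for low-risk women is not a true maximum: the protocol's own schedules allow 3 years, and more for some women

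*Protocol*

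**What the plan says.** Section 12.3 describes participants in the low-risk category ("and above the onset age for standard breast screening in their country) will have less frequent breast imaging comparatively to standard practices") and states that for them "the detection of potential cancer could be delayed of a maximum of 2 years as compared to the standard screening frequency". It refers the reader to section 1.2.3, which compares 4-yearly with 2-yearly mammograms.

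The schedules are set elsewhere in the protocol:

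- **Low risk (section 5.2.5):** "Women identified at low risk will not have any mammogram until an end of study mammogram at 4 years".
- **Average risk (section 5.2.5):** "Women at average risk will have a mammogram every 2 years". This applies at any age.
- **Standard arm (Synopsis Table 2; section 5.1):** every 2 years at 50-70 in France, Belgium, Italy and Israel, every 3 years at 50-70 in the UK, and every year in the column headed "45-49 (Some regions of Italy").
- **Dating of the next mammogram (section 1.1.14):** "This will be dated from the date of her most recent mammogram in the two years prior to enrollment into the trial". By default no mammogram is done at entry. In the worked example, a woman on a 2-yearly schedule whose last mammogram was a year before entry "would be invited to screen again one year after enrollment into the study". Section 7.4 also plans the schedule from the previous mammogram.

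Section 12.4 asks for the number and frequency of cancers overall and in the low-risk subgroup, "as well as the stage of the cancer and evaluate if these participants are disadvantaged or not".

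**The concern.** Section 12.3 gives an upper limit, so a single schedule in the protocol that exceeds it makes the statement wrong. Two features appear to do so. The standard arm includes a yearly schedule that a 4-minus-2 calculation leaves out. And a low-risk woman's mammogram is fixed at year 4 from randomization, while her standard mammogram would have been dated from an examination that may lie well before entry.

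What is at stake is the accuracy of the worst case that the safety section gives for women who are deliberately screened less. Ethics committees read that section, and the EDMC is asked to judge whether these women are disadvantaged.

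A smaller matter is that section 12.3 names only low-risk women as less screened. Average-risk women aged 45-49 in the yearly Italian regions also move to a longer mammogram interval.

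**Working it through.** **Inputs.** The low-risk mammogram is at month 48 (section 5.2.5). The standard interval I is 12, 24 or 36 months (Synopsis Table 2). The last mammogram was m months before entry, with m from 0 to 24 (section 1.1.14; the schedule of activities accepts reference mammograms up to 2 years old). The protocol gives no distribution for m, so it is shown over a range.

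**Reproducing the stated figure on nominal intervals.**

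- 2-yearly countries: 4 - 2 = 2 years, which is the protocol's figure.
- UK: 4 - 3 = 1 year, so 2 years is conservative.
- Yearly Italian regions, 45-49: 4 - 1 = 3 years, so 2 years is too low.

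**With the dating rule.** The first standard mammogram that is forgone falls at month I - m. The possible delay is 48 - (I - m) months, that is:

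- 2-yearly: 48 - (24 - m) = 24 + m
- UK 3-yearly: 48 - (36 - m) = 12 + m
- yearly Italian regions: 48 - (12 - m) = 36 + m

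The risk result arrives at 8-12 weeks (section 5.2), so only mammograms due at month 3 or later are counted as forgone. This limits m to 21 on the 2-yearly schedule and to 9 on the yearly one.

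| Standard schedule | m = 0 | Intermediate m | Largest m counted |
|---|---|---|---|
| 2-yearly | 48 - 24 = 24 | m = 12: 48 - 12 = 36 | m = 21: 48 - 3 = 45 |
| UK 3-yearly | 48 - 36 = 12 | m = 12: 48 - 24 = 24 | m = 24: 48 - 12 = 36 |
| Yearly (Italy, 45-49) | 48 - 12 = 36 | m = 3: 48 - 9 = 39 | m = 9: 48 - 3 = 45 |

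The 2-yearly entry at m = 12 is the example in section 1.1.14. On that schedule 24 months is the smallest value in the range counted. In the UK the stated limit holds for m up to 12.

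**Does a baseline mammogram reset the clock?** Section 5.2.3 makes one mandatory at age 50 or over only when density is unavailable. Density is otherwise taken from the most recent mammogram. Women who get the baseline mammogram have m = 0 and return to about 24 months (UK 12). The others do not.

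**Average-risk women, 45-49, yearly Italian regions.** For a woman up to date with yearly screening (m at most 12), the difference is (24 - m) - (12 - m) = 12 months.

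**The case against.** The strongest reply is that section 12.3 speaks of screening frequency and refers to section 1.2.3, which sets 4-yearly against 2-yearly mammograms. Section 8.3.1 also labels the low-risk schedule as one mammogram every 4 years. On that reading the 2-year figure is right for four countries at 50-70 and conservative in the fifth. This stands, and it means the dating-rule figures are not the only way to read the sentence. It does not rescue the yearly Italian regions, where nominal intervals already give 3 years.

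One could add that the onset age is defined by country, whereas screening at 45-49 is regional in Italy. That would make the sentence true of the women it covers, but only by leaving out the low-risk women with the longest nominal delay.

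On the average-risk group, a delay of about 1 year lies within the stated 2 years. The loss of mammograms is partly offset, because the risk-based arm adds ultrasound for dense breasts (section 1.1.17) and the Italian programme does not include it. Section 9.2 lets the EDMC demand any analysis, and section 3.2.3 plans subgroup analyses by country, risk and age. All of this stands, so this part is only a minor addition.

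A reader might infer that monitoring of low-risk women is compromised, or that the trial's results are at risk. The documents support neither. No EDMC step or threshold depends on the 2-year figure. Low-risk cancers are reviewed at EDMC meetings held at least yearly (section 12.3) and reported to the French authority (section 12.2).

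**Conclusion.** The 2-year maximum is wrong as written. On nominal intervals it fails only for women aged 45-49 in the yearly Italian regions (3 years). Under the protocol's dating rule it also fails for 2-yearly women whose last mammogram preceded entry (24 + m months) and for UK women with m above 12 (12 + m).

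The dating-rule figures rest on three assumptions: the end-of-study mammogram is at exactly 48 months, the standard mammogram is taken when due, and the first forgone mammogram falls at month 3 or later. In the yearly regions it must also fall due before the woman reaches 50 and moves to the 2-yearly standard.

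These are possible delays in screen detection. A reader might take them as expected delays in diagnosis, but symptoms may bring diagnosis forward, and the sentence at issue states a maximum. Nor can it be said how many women exceed 24 months, since the protocol gives neither the distribution of m nor the number of women in the yearly Italian regions.

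Endpoint, schedules, sample size and analysis are unaffected. This is a correction to a safety statement, and minor in scale.

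**What to change.** In section 12.3, replace the 2-year maximum with the possible delay by standard schedule (yearly, 2-yearly, 3-yearly) and date of last mammogram. State that it can reach 3 years and exceed it for some women.

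As a minor addition in sections 12.3 and 12.4, extend the EDMC listing of less-screened women to any other woman in the risk-based arm whose assigned mammogram interval is longer than the standard applicable to her age and region, as updated during the trial. At present this means average-risk women aged 45-49 in the yearly Italian regions.

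The cost is protocol wording and one derived flag. Region would come from the enrolling centre, because section 11.1.4 does not list it among the baseline data. The downside is a less favourable stated delay and a slightly longer EDMC listing. No woman's schedule changes.
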